Participants randomized to the treatment sequence placebo-cladribine, will receive their first 5-day cladribine treatment in Study Period 2 (Days 9 to 13), and will receive their second 5-day cladribine treatment between 28 to 35 days thereafter, which conforms to the approved cladribine posology. It is important to note, that this second cladribine treatment week will not be part of the study itself but provided as standard medical care of participants in the following month after end of the study (see Section 6.7).

Participants randomized to the treatment sequence cladribine-placebo, will receive their first 5-day cladribine treatment in Study Period 1 (Days 9 to 13). Since, according to the study design, they will have to receive Placebo treatment 4 weeks thereafter (i.e., Study Period 2, Days 9 to 13), their second 5-day cladribine treatment will have to be deferred by 6 days (i.e., Study Period 2, Days 15 to 19). Accordingly, participants will receive their second 5-day cladribine treatment 34 days after having received their first cladribine 5-day treatment in Study Period 1. This schedule will only marginally deviate from the approved cladribine posology. In view of the long-lasting duration of action of cladribine, this modest deferral of the second cladribine treatment week is unlikely to affect the overall efficacy of cladribine treatment.

The second cladribine treatment on Days 15 to 19 in Study Period 2 will not alter the primary study objectives, as the treatment is only initiated after all PK and  samples will have been taken on Day 14 with the last sampling in the morning of Day 15 (initiation of second cladribine treatment thereafter).

In order to also enable blinding of the Days 15 to 19 cladribine treatment in Study Period 2, all participants from both treatment sequences will receive placebo on Days 15 to 19 in Study Period 1, and participants randomized to the treatment sequence cladribine-placebo (Days 9 to 13) will receive cladribine on Days 15 to 19 in Study Period 2 as their second dose (see Section 1.2, Figure 1).

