5.4 Screen Failures

Individuals who do not meet the criteria for participation in this study (screen failure) may be rescreened. Rescreened participants will be assigned a new participant number.

6 Study Intervention(s)

Study intervention is any investigational intervention(s), marketed product(s), placebo, or medical device(s) intended to be administered to a study participant per the study protocol.

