6.7 Study Intervention after the End of the Study

The dose and the posology of both the examined treatments, cladribine tablets and the monophasic oral contraceptive Microgynon as per this study protocol will be consistent with the labeled use of both products. The study design ensures that participants would be able to receive the full dose and dosage regimen as per label with only minimum deviations, as further described in Section 4.1 and below.

Study participants will be offered the approved 2-year use of cladribine. Following completion of the 2 annual treatment courses, no further cladribine treatment is required in years 3 and 4.

Participants randomized to the treatment sequence cladribine-placebo will receive their first and second 5-day repeat-dose treatments as part of their study participation.

For participants randomized to the treatment sequence placebo-cladribine, only the first cladribine 5-day treatment will be part of the study, while the second cladribine 5-day treatment will be offered to the study participants as medical care in the month after end of study provided by the Sponsor.

Further on, 1 year after having received the first dose of cladribine of the first 5-day repeat-dose treatments (as part of the study), participants will embark into treatment course 2 which also consists of 2 5-day repeat-dose treatments, 1 at the beginning of the first month and 1 at the beginning of the second month of the second treatment year. Cladribine treatment will be provided by the Sponsor outside of the study.

Study participants that enter the study as their second year treatment course (see Section 6.5.3) will complete their full 2-year treatment course during or shortly after the End of Study Visit, and no further treatment will be provided by the Sponsor.

Principal Investigators will be informed of the treatment sequence of each participant once a participant has completed the End of Study Visit, as they need to know whether another dose of cladribine needs to be given. Details on this procedure are described in the IMP Handling Manual.

Criteria for initiating and continuing cladribine therapy are as follows:

Lymphocyte counts must be

- normal before initiating cladribine treatment in Study Period 1 of the study;
- at least 800 cells/mm³ before initiating cladribine treatment in year 2.

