If necessary, the treatment course in year 2 can be delayed for up to 6 months to allow for recovery of lymphocytes. If this recovery takes more than 6 months, the participant should not receive cladribine anymore.

With respect to treatment with Microgynon, contraceptive measures may or may not be altered after end of the study as per preference of treating physician and participant. In any case, after conclusion of the study effective contraception (e.g., by taking a hormonal oral contraceptive or applying another highly effective birth control method) starting 1 month after last dose of study intervention must be used and continue for at least 5 months (see Inclusion Criterion #11, and Appendix 3).

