Appendix 3 Contraception

Woman of Childbearing Potential (WOCBP)

A woman is of childbearing potential (i.e., fertile), following menarche and until either:

- 1) Becoming postmenopausal; or,
- 2) is permanently sterile by means of a hysterectomy, bilateral salpingectomy or bilateral oophorectomy.

Postmenopausal is defined as no menses for 12 months without an alternative medical cause. A high follicle stimulating hormone (FSH) level in the postmenopausal range may be used to confirm a postmenopausal state in women not using hormonal contraception or hormonal replacement therapy. However, in the absence of 12 months of amenorrhea, a single FSH measurement is insufficient.

Highly Effective Contraceptive Methods

A highly effective contraceptive method must be applied from enrollment to 1 month after last dose of study intervention.

Highly effective methods are those with a failure rate of less than 1% per year when used consistently and correctly.

These methods are further classified into user-independent and user-dependent methods. Because user-independent methods do not depend on the participant's ability to use them consistently and correctly, they are preferred when contraception is introduced as a condition for study participation.

Caution should be taken for hormonal contraception, as it may be susceptible to interaction with the study intervention(s), which may reduce the efficacy of the contraception method. Hence, a second highly effective method of contraception should be used from enrollment to 1 month after last dose of study intervention.

Highly effective contraceptive methods, to be used in addition to the hormonal contraceptive (Microgynon) as per this study protocol are listed below:

Permitted:

User-Independent

- Intrauterine device (IUD)
- Bilateral tubal occlusion
- Vasectomized partner: This is a highly effective contraception method only if the partner is the sole sexual partner of the WOCBP and he has received medical assessment of the surgical success

- Sexual abstinence: This is a highly effective method only if the WOCBP refrains from heterosexual intercourse during the entire period of risk associated with the study intervention. The reliability of sexual abstinence needs to be evaluated in relation to the duration of the study and the preferred and usual lifestyle of the participant.

Not permitted, since they would interfere with the study objective:

User-Dependent

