- Combined (estrogen- and progestogen-containing) hormonal contraception associated with inhibition of ovulation
 - Oral
 - Intravaginal
 - Transdermal
- Progestogen-only hormonal contraception associated with inhibition of ovulation
 - Oral
 - Injectable

User-Independent

- Implantable progestogen-only hormonal contraception associated with inhibition of ovulation
- Intrauterine hormone-releasing system (IUS)

Effective Contraceptive Method

An effective contraceptive method must be used starting 1 month after last dose of study intervention and continue for at least 5 months.

Allowed only under certain situations as specified in the Clinical Trial Facilitation Group (CTFG) recommendations, because they have a failure rate of **more than** 1% per year and therefore are not considered to be highly effective methods.

- Male or female condom with or without spermicide
- Cap, diaphragm or sponge with spermicide
- Combination of a male condom with cap, diaphragm or sponge with spermicide (i.e., double barrier method)

Appendix 4 Adverse Events: Definitions and Procedures for Recording, Evaluating, Follow-up, and Reporting

Definitions

Adverse Event

An AE is any untoward medical occurrence in a participant administered a pharmaceutical product, regardless of causal relationship with this treatment. Therefore, an AE can be any unfavorable and unintended sign (including an abnormal laboratory finding), symptom, or disease temporally associated with the use of a medicinal product, regardless if it is considered related to the medicinal product.

For surgical or diagnostic procedures, the condition/illness leading to such a procedure is considered as the AE rather than the procedure itself.

The Investigator is required to grade the severity of each AE.

Investigators must assess the severity of AEs per the Qualitative Toxicity Scale, as follows:

- Mild:** The participant is aware of the event or symptom, but the event or symptom is easily tolerated.
- Moderate:** The participant experiences sufficient discomfort to interfere with or reduce his or her usual level of activity.
- Severe:** Significant impairment of functioning: the participant is unable to carry out his or her usual activities.

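### Read literally, the contraception rule lets placebo-cladribine women stop the second method 1 to 10 days after their last cladribine tablet, not 28 to 30

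*Protocol*

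**What the plan says.** Three places in the protocol set the contraception rule, and all three use the same anchor.

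- **Appendix 3** asks that "a second highly effective method of contraception should be used from enrollment to 1 month after last dose of study intervention". For the lower tier it says: "An effective contraceptive method must be used starting 1 month after last dose of study intervention and continue for at least 5 months".
- **Inclusion Criterion 11** keeps highly effective contraception in place for a minimum of 4 weeks past the last dose of study intervention. After that it accepts an effective method, with an oral contraceptive as its example.
- **Section 6.7**, which covers the time after the study, gives the same step: "applying another highly effective birth control method) starting 1 month after last dose of study intervention must be used". It also leaves changes to contraception after the study to the physician and participant.

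The opening of Section 6 defines study intervention as products "intended to be administered to a study participant per the study protocol", and the Section 6.1 table lists Microgynon among them. Section 4.2 says of the placebo-cladribine sequence that "this second cladribine treatment week will not be part of the study itself but provided as standard medical care of participants", and that these women "will receive their second 5-day cladribine treatment between 28 to 35 days thereafter". Section 6.7 agrees: only the first week belongs to the study, and "the second cladribine 5-day treatment will be offered to the study participants as medical care in the month after end of study". Sections 4.1 and 8 count 5 cladribine days for this sequence and 10 for the other.

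**The concern.** The anchor and the drug exposure come apart in one of the two sequences. In cladribine-placebo, both cladribine weeks fall inside the study, so the last study intervention is also later than the last cladribine tablet. In placebo-cladribine, the second cladribine week comes after the End of Study Visit and is described as standard care. A clock that starts at the last study dose is therefore already running when that week begins.

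The protocol's own reasons make this matter. Section 4.2 reports teratogenic effects of cladribine in preclinical studies. Appendix 3 explains why a second method is needed: "Caution should be taken for hormonal contraception, as it may be susceptible to interaction with the study intervention(s), which may reduce the efficacy". That possible interaction is the question the trial is designed to answer, so it cannot be assumed absent when the step-down is set. Exclusion Criterion 33, on oocyte donation, counts its 6 months from the last cladribine dose, so the protocol already uses the safer anchor elsewhere.

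**Working it through.** All days are on the Study Period 2 scale, with 28-day periods (Section 4.1). A month is taken as 30 days (assumption).

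**1. Counting convention.** Section 4.2 states 34 days between the two cladribine weeks of the cladribine-placebo sequence. Period 1 Day 9 is Day 9 − 28 = −19, and the second week starts on Day 15: 15 − (−19) = 34. The stated figure is reproduced, so the protocol counts from start to start.

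**2. Second week, placebo-cladribine.** The first week is Days 9 to 13. The second starts on 9 + 28 = Day 37 to 9 + 35 = Day 44. The last tablet is 4 days later: Day 41 to Day 48.

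**3. Step-down day.** The last in-study dose is Microgynon on Day 21.
- 4 weeks (Inclusion 11): 21 + 28 = Day 49.
- 1 month (Appendix 3, Section 6.7): 21 + 30 = Day 51.

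**4. Highly effective cover after the last cladribine tablet.** Shortest: 49 − 48 = 1 day. Longest: 51 − 41 = 10 days (11 with a 31-day month). The rule aims at 28 to 30.

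**5. The other sequence.** Its last cladribine tablet is on Day 19: 49 − 19 = 30 to 51 − 19 = 32 days. There is no shortfall.

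**6. Minimum total cover.** One plus five months from Day 21 ends on 21 + 180 = Day 201. After the last cladribine tablet that leaves 201 − 48 = 153 to 201 − 41 = 160 days, against about 180.

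**7. Other readings of the anchor and the interval.** A negative value means the rule allows step-down before the last tablet.

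| Last study intervention taken as | 28–35 days counted from Day 9 | 28–35 days counted from Day 13 |
|---|---|---|
| Microgynon, Day 21 | 1 to 10 days | −3 to 6 days |
| Placebo tablet, Day 19 | −1 to 8 days | −5 to 4 days |
| In-study cladribine, Day 13 | −7 to 2 days | −11 to −2 days |

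The 1 to 10 days is the most favourable result among the readings that leave the second week outside the study. If that week is study intervention, the gap is zero.

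**8. Women affected.** The planned number is redacted. Section 7.2 gives 16 evaluable women and 18% to 30% drop-out: 16 / 0.82 = 19.5 and 16 / 0.70 = 22.9, or about 20 to 23 entrants. At 1:1 that is about 10 to 12 in this sequence. Women who leave before receiving cladribine, and those without childbearing potential (eligible under Inclusion 11), are not at risk.

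**The case against.** The strongest objection is that the post-study week may itself be study intervention. Section 6.7 is headed as dealing with study intervention after the study, and the contraception sentence sits in that section. The sponsor supplies the tablets, and the packaging entry in Section 6.1 covers both the study and the first-year medical care. On that reading there is no gap. The heading does allow it, but no passage states it, and Sections 4.1, 4.2, 6.3.2, 6.6.1 and 6.7 all treat the week as care outside the study. At best the rule is ambiguous.

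A second objection is that the week is given under the product label, and a physician would follow the label's contraception advice. Section 2.3 mentions non-hormonal, effective methods for at least 6 months. The label, the consent form and the IMP Handling Manual are not available here, so actual practice cannot be judged. Section 6.7 nonetheless sets its own post-study rule, and that rule should be right.

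A third objection stands and limits the point. A reader might infer that these women will lose protection within days. The documents do not support that. The permitted second methods are an IUD, tubal occlusion, a vasectomized partner or abstinence. The first three would usually persist, and Appendix 3 accepts abstinence only if it lasts through the whole period of risk. The durations are minimums, and an effective method is still required for 5 months after step-down.

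A reader might also size the risk as half of the 16 evaluable women. That figure counts women evaluable for bioequivalence, whereas a contraception risk applies to every woman of childbearing potential who is dosed.

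**Conclusion.** The point holds as a defect in the anchor of a safety rule. Taken literally, the text permits placebo-cladribine women to stop the second highly effective method 1 to 10 days after their last cladribine tablet instead of 28 to 30. The minimum total cover is 153 to 160 days instead of about 180. This rests on three assumptions: the second week is outside the study, as Sections 4.2 and 6.7 say; the last study intervention is Microgynon on Day 21; and the 28 to 35 days run from start to start, as the protocol's 34 days imply. Moving the anchor to Day 19 or Day 13, or counting the interval from Day 13, gives less cover. Counting the second week as study intervention removes the gap.

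At most about 10 to 12 women are concerned, under the stated drop-out range, and fewer in practice. No endpoint, estimate or bioequivalence conclusion changes. The wording should still be corrected, because the drug was teratogenic in preclinical studies and the efficacy of the remaining oral contraceptive is the open question.

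**What to change.** In the contraception text of Inclusion Criterion 11, Section 6.7 and Appendix 3, replace the anchor with: *last dose of study intervention or last dose of the second cladribine week given after the End of Study Visit, whichever is later*. This cannot shorten anyone's window and leaves the cladribine-placebo sequence unchanged.

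At the unblinding step that already follows each End of Study Visit (Section 6.3.2), have the site tell placebo-cladribine women to keep the second method until 1 month after that cladribine week.

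Step-down then moves to Day 69–76 (41 + 28 to 48 + 28) or Day 71–78 (41 + 30 to 48 + 30). The cost is 69 − 49 = 20 to 76 − 49 = 27 more days of the second method for the women affected, plus wording edits in three places and one instruction. No visit or sample is added.

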Appendix 5 Clinical Laboratory Tests

Clinical laboratory tests utilized for the study are shown in the table below.

Table 8 Protocol-Required Clinical Laboratory Assessments

Laboratory Assessments	Parameters			
Hematology	Platelet Count		RBC Indices: 
 • MCV • MCH • %Reticulocytes 	WBC Count with Differential: 
 • Neutrophils • Lymphocytes • Monocytes • Eosinophils • Basophils
	RBC Count			
	Hemoglobin			
	Hematocrit			
Clinical Chemistry	BUN	Potassium	Aspartate aminotransferase (AST) / serum glutamic-oxaloacetic transaminase (SGOT)	Total and direct bilirubin
	Creatinine	Sodium	Alanine aminotransferase (ALT) /serum glutamic-pyruvic transaminase (SGPT)	Total Protein
	Glucose (fasting)	Calcium	Alkaline phosphatase	Uric acid
	Amylase	Lipase	γ-Glutamyl-transferase	Triglycerides
	Lactate dehydrogenase	Creatine phosphokinase	Urea	LDL-/HDL-cholesterol and cholesterol
Urinalysis	
 • Specific gravity • pH, glucose, protein, blood, ketones, bilirubin, urobilinogen, nitrite, leukocyte esterase by dipstick • Microscopic examination (if blood or protein is abnormal). Only if blood, protein, nitrite, or leukocyte esterase are positive on the dipstick • Urine pregnancy test (as needed for women of childbearing potential) 			
Other Tests	
 • Serum human chorionic gonadotropin (hCG) pregnancy test (as needed for women of childbearing potential). • Serology (HIV 1 and 2 antibody (anti-HIV1/2), hepatitis B surface antigen (HbsAG), hepatitis B core antibody (HbcAb), hepatitis C virus (anti-HCV) and Herpes Zoster • QuantifERON®-TB Gold or Gold Plus test • Alcohol breath test, • TSH • Urine drug screen: 
 • Cocaine • Amphetamines • Methamphetamines • Opiates • Barbiturates • Ecstasy • Benzodiazepine • Methadone • Cannabinoids • Phencyclidine • Tricyclic antidepressants 			

ALT=alanine aminotransferase; AST=aspartate aminotransferase; BUN=blood urea nitrogen; HbcAB=hepatitis B core antibody; HbsAG=hepatitis B surface antigen; hCG=human chorionic gonadotropin; HCV=hepatitis C virus; HDL=high density lipoprotein; HIV=human immunodeficiency virus; LDL=low density lipoprotein; MCH=mean corpuscular hemoglobin; MCV=mean corpuscular volume; RBC=red blood cell; SGOT=serum glutamic-oxaloacetic transaminase; SGPT=serum glutamic-pyruvic transaminase; TSH = thyroid stimulating hormone, WBC=white blood cell

Appendix 6 Pharmacokinetic Parameters

Symbol	Definition
AUC_{τ}	The area under the concentration-time curve (AUC) over the dosing interval from $T_1=0$ hours to $T_2=\tau$ h. Calculated using the mixed log linear trapezoidal rule (linear up, log down). For single dose, AUC_{τ} is calculated as a partial area with the defined time range. In multiple dose profiles AUC_{τ} is calculated at steady state from 1 predose time point to the dosing interval time. In cases where the actual observation time is not equal to the scheduled observation time AUC_{τ} will be calculated based on the estimated concentration at τ hours, and not the concentration at the actual observation time.
C_{av}	The average concentration at steady state. $C_{av} = AUC_{\tau} / \tau$.
C_{pre}	Measured concentration at the end of a dosing interval during repeat-dosing (taken directly before next administration)
C_{max}	Maximum observed concentration
C_{min}	The minimum observed concentration during a complete dosing interval
C_{trough}	The concentration observed immediately before next dosing (corresponding to predose or trough concentration for multiple dosing)
PTF%	The peak trough fluctuation within a complete dosing interval at steady state. $PTF = 100 * (C_{max} - C_{min}) / C_{av}$.
t_{max}	The time to reach the maximum observed concentration collected during a dosing interval (unless otherwise defined, take the first occurrence in case of multiple/identical C_{max} values)
t_{min}	The time to reach the minimum observed concentration collected during a dosing interval
τ	Dosing interval

Appendix 7 Protocol Amendment History

The information for the current amendment is on the title page.

Non-substantial amendment 3 to the original protocol (CSP v4.0, version date: 20 November 2020)

Section # and Name	Description of Change	Brief Rationale
5.2 Exclusion Criteria	Specified exclusion criterion #19	Wash-out requirements/procedures for additional medications added

Non-substantial amendment 2 to the original protocol (CSP v3.0, version date: 06 April 2020):

Section # and Name	Description of Change	Brief Rationale
1.1 Synopsis, Overall Design 1.3 Schedule of Activities	Clarified wording for extended Screening period due to a delayed menstrual cycle and laboratory value(s) re-testing	Clarification of process
1.2 Schema, Figure 1 Study Design Diagram	██████ of study design diagram to clarify wording	Clarification of process
1.3 Schedule of Activities	Weight control added on Day 21 of Run-in-Period and Day 21 of Study Period 1 Minor formatting revision	Ability to calculate/adapt dosage of study intervention accordingly to actual weight Minor corrections
4.1 Overall Design	Clarified wording for extended Screening period due to a delayed menstrual cycle and laboratory value(s) re-testing Correction of recruitment phase from "12 months" to "21 months" and total clinical duration of the study from "16 months" to "25 months"	Clarification of process
4.2 Scientific Rationale for Study Design	Extension of time window to "between 28 to 35 days" for the second 5-day cladribine treatment (medical care) for Sequence 2 (placebo-cladribine) For Sequence 1 (cladribine-placebo) change of wording from "Accordingly, participants will receive their second 5-day cladribine treatment 4 weeks and 6 days after ..." to "Accordingly, participants will receive their second 5-day cladribine treatment 34 days after ...".	Clarification of study rationale To be in alignment with the wording in the section
6.3.2 Blinding	To further detail wording for the unblinding process after the End of Study	Clarification of process
6.3.3 Emergency Unblinding	Clarified wording for recording the date and reason for unblinding	Clarification of process

Section # and Name	Description of Change	Brief Rationale
6.4 Study Intervention Compliance	Clarified wording for assessment of compliance	Clarification of process
6.7 Study Intervention after the End of the Study	Clarified wording for informing Principal Investigators of the treatment sequences once participants have completed the End of Study Visit	Clarification of process
8.2.1 Physical Examination	Weight control added on Day 21 of Run-in-Period, Day 21 of Study Period 1 and Day 8 of Study Period 2	Alignment with Section 1.3 Schedule of Activities
8.2.4 Clinical Safety Laboratory Assessments	Clarified wording for extended Screening period due to laboratory value(s) retesting	Clarification of process
9.3 Populations for Analyses	First paragraph rephrased to clarify participants of the data review meeting	Clarification of process
Appendix 2 Study Governance	Sentence deleted “• Definition of what constitutes source data is found in the Data Management Plan”	Clarification of which definition is given in the Data Management Plan
Whole document	Minor editorial and document formatting revisions	Minor corrections; therefore, have not been summarized

Non-substantial amendment 1 to the original protocol (CSP v2.0, version date: 04 July 2019):

Section# and Name	Description of Change	Brief Rationale
5.1 Inclusion Criteria	
The safety blood sample, including hematology assessments, was moved from Day 9 of Study Period 1 to Day 21 of Run-in-Period.
 
This assures that results of the safety laboratory including hematology are in place before start of IMP treatment for fulfillment of inclusion criterion #4.
 
Lymphocyte requirements (inclusion criterion #4) were differentiated for treatment in year 1 and year 2.
 
Range definition for white blood cell counts, absolute lymphocyte counts and absolute neutrophil counts was changed from strictly normal range to normal range (applies for patients in year 1).
	In order to clarify inclusion criterion #4 in Section 5.1.
6.3.1 Study Intervention Assignment	
The randomization of participants was moved from Day 8 of Study Period 1 to Day 21 of Run-in-Period.
 
This assures that participant’s assigned study intervention is available at site in time.
	In order to correct time point of randomization in Section 6.3.1.
Whole document	Minor editorial and document formatting revisions	Minor corrections

